8.8.2 Optional Samples

Tissue Biopsies

Optional tissue biopsies may be taken at any time point per Investigator's discretion and with participant's consent, for example due to skin-related AEs, disease progression, or long-lasting stable disease, to aid the understanding of immune resistance or homeostasis mechanisms. At the discretion of the Investigator, obtaining a healthy tissue alongside the symptomatic/pathological site would be desirable in order to serve as control tissue. In the case of skin related AEs, skin biopsies should be obtained from the sites of symptomatic skin as well as from an unaffected site of the skin serving as control tissue for histological- and immuno-histochemical examination.

Assessments as well as biological samples, which are not protocol-specified and are conducted by the Investigator in response to an AE (e.g. laboratory tests, etc.) can be performed at any time during the study and the results may be shared with the Sponsor in order to further inform about the safety profile of RO7296682.

The informed consent form will contain a separate section that addresses the use of remaining mandatory samples for optional exploratory research. A separate signature will be required to document a participant's agreement to allow any remaining samples to be used for exploratory research.

Optional tumor and/or healthy samples will be destroyed within 2 years after the date of final closure of the clinical database.

8.9 SAMPLES FOR RESEARCH BIOSAMPLE REPOSITORY

8.9.1 Overview of the Research Biosample Repository

The Roche Research Biosample Repository (RBR) is a centrally administered group of facilities for the long-term storage of human biologic samples, including body fluids, solid tissues, and derivatives thereof (e.g., DNA, RNA, proteins, peptides). The collection, storage, and analysis of the RBR samples will facilitate the rational design of new pharmaceutical agents and the development of diagnostic tests, which may allow for individualized drug therapy for patients in the future.

8.9.2 Sample Collection

DNA and RNA RBR samples will be collected from participants who give specific consent to participate in this optional RBR during C1D1. Collected specimens will be used to achieve the following objectives:

- To study the association of biomarkers with efficacy, AEs, or progressive disease.
- To increase knowledge and understanding of disease biology.
- To study treatment response, including drug effects and the processes of drug absorption and disposition.

- To develop biomarker or diagnostic assays and establish the performance characteristics of these assays.

In addition, the following samples will be stored in the RBR and used for research purposes, including, but not limited to, research on biomarkers related to study treatment or diseases:

- Leftover plasma samples
- Leftover serum samples
- Leftover blood samples
- Leftover tumor samples

Optional Stool Samples

In Part B, dose expansion, participants will be given the option of consenting to provide stool samples. Dietary intake is a central determinant of changes in the microbiota, which influences the immunological responses in the intestine and thereby impacting potential AEs during immunotherapies. A nutritional assessment may therefore be performed at baseline to better correlate the profiles of the microbiota to safety-relevant immune responses.

Upon consent, participants will be requested to provide optional stool samples at the following time points:

- At screening, any time prior to C1D1
- On-treatment, every 12 weeks (± 14 days)
- Upon occurrence of colitis, as assessed and confirmed by the Investigator

Additional stool samples may be requested at any time point per Investigator's discretion, for example when resuming treatment post colitis.

For sampling procedures, storage conditions, and shipment instructions, see the sample flowchart and additional instruction documents.

Optional stool samples will be destroyed within 2 years after the date of final closure of the clinical database.

8.9.3 Leftover of Sample Derivatives such as DNA and RNA

The samples collected for DNA extraction include, but is not limited to, genomic analysis and may be sent to one or more laboratories for analysis of germline or somatic mutations via whole genome sequencing (WGS), whole exome sequencing (WES), next-generation sequencing (NGS), or other genomic analysis methods.

Genomics is increasingly informing researchers' understanding of disease pathobiology. WGS and WES provide a comprehensive characterization of the genome and exome, respectively, and, along with clinical data collected in this study, may increase the opportunity for developing new therapeutic approaches or new methods for monitoring efficacy and safety or predicting which participants are more likely to respond to a drug or develop AEs. Data will be analyzed in the context of this study but will also be explored in aggregate with data from other studies. The availability of a larger dataset will assist in identification of important pathways, guiding the development of new targeted agents.

Samples may be sent to one or more laboratories for analysis for of germline or somatic mutations via WGS/WES, or other genomic analysis methods. Participants will not be identified by name or any other personally identifying information. Data generated from RBR samples will be analyzed in the context of this study but will also be explored in aggregate with data from other studies. The availability of a larger dataset will assist in identification and characterization of important biomarkers and pathways to support future drug development. Given the complexity and exploratory nature of these analyses, WGS/WES data and analyses will not be shared with Investigators or study participants unless required by law.

For all samples, dates of consent and sample collection should be recorded on the associated RBR page of the eCRF. Details on processes for collection and shipment of these samples can be found in separate Laboratory Manual.

RBR samples will be stored and used until no longer needed or until they are exhausted. The Research Biosample Repository storage period will be in accordance with the IRB/EC-approved Informed Consent Form and applicable laws (e.g., Health Authority requirements). The repository samples will be subject to the confidentiality standards (as described under Confidentiality and in [Appendix 1](#)).

8.10 HEALTH ECONOMICS/MEDICAL RESOURCE UTILIZATION AND HEALTH ECONOMICS

Health Economics/Medical Resource Utilization and Health Economics parameters are not evaluated in this study.

8.11 TIMING OF STUDY ASSESSMENTS

8.11.1 Screening and Pre-treatment Assessments

Written informed consent for participation in the study must be obtained before performing any study-specific screening tests or evaluations. ICFs for enrolled participant and for participants who are not subsequently enrolled will be maintained at the study site.

All screening, and all pre-treatment assessments (related to entry criteria), must be completed and reviewed to confirm that participants meet all eligibility criteria. The

Investigator will maintain a screening log to record details of all participants screened and to confirm eligibility or record reasons for screening failure.

An Eligibility Screening Form documenting the Investigator's assessment of each screened participant with regard to the protocol's inclusion and exclusion criteria is to be completed by the Investigator and kept at the investigational site.

Screening and pretreatment assessments will be performed according to the SoA outlined in Section 1.3. Serum pregnancy test will be done 7 days prior to C1D1. Where the clinical significance of an abnormal screening test result (lab or any other tests) is considered uncertain, the test may be repeated. Screening tumor assessments performed in a reasonable time window prior to Informed Consent Form signature can be accepted if agreed with the Sponsor and if done as standard of care and according to RECIST v1.1 and iRECIST in a qualified facility in which all further scans for the participant will be performed (as defined in Appendix 7 and Appendix 8).

8.11.2 Assessments during Treatment

Under no circumstances will participants who enroll in this study and have completed treatment as specified, be permitted to re-enroll in the study.

All assessments must be performed as per SoA (Section 1.3). Assessments scheduled on the day of study treatment administration should be performed prior to administration of study treatment, unless otherwise noted in the schedule of assessments.

Participants will be treated with study treatment, until disease progression, unacceptable toxicity, withdrawal of consent, or withdraw by Investigator. Participants may receive study treatment for a maximum of 24 months since C1D1.

8.11.3 Assessments at Study Completion/Early Termination Visit

End of Treatment/Early Discontinuation: Participants who complete the study or discontinue from the study early, will be asked to return to the clinic 28 (\pm 7) days after the last dose of study drug or last data point. The visit at which a response assessment shows progressive disease may be used as the Early Discontinuation visit. Assessments should be completed as detailed in the SoA (Section 1.3).

8.11.4 Follow-Up Assessments

Safety Follow-Up/End of Study: Participants who complete the treatment or discontinue from the study early, will be asked to return to the clinic 90 (\pm 7) days after the last dose of study drug or last data point determined for an End of Study Visit. Assessments should be completed as detailed in the SoA (Section 1.3).

Survival Follow-Up: The sites will provide to the Sponsor an update on survival status and new anti-cancer treatment 90 (\pm 7) days after the Safety Follow-Up visit and then every 3 months (\pm 2 weeks) thereafter up until 24 months post initial treatment (or until study closure) for each participant enrolled in the study. Contact can be either in person

or via a phone call to document; the sites will use a designated section of the eCRF for this purpose.

After the study completion/early termination visit, AEs should be followed, as outlined in Section 8.3.1 and Section 8.3.3.

8.11.5 Assessments at Unscheduled Visits

For activities that are required to be performed in case of an unscheduled visit, see Section 1.3.

9. STATISTICAL CONSIDERATIONS

9.1 STATISTICAL HYPOTHESES

No formal statistical model and no formal hypothesis testing are planned in this study.

9.2 SAMPLE SIZE DETERMINATION

- Part A:

The maximum total number of participants in the dose escalation portions of Part A will be approximately 90 DLT evaluable participants on a Q3W schedule. The exact sample size cannot be pre-determined and depends on the number of cohorts needed to reach a MTD and/or RP2D. The simulations presented in Section 3 of [REDACTED] show however simulated sample sizes in a variety of toxicity scenarios.

- Part B:

Up to a maximum of 50 participants may be enrolled in the expansion cohort in Part B. Participants with MEL, NSCLC and HNSCC which are not amenable to standard treatment, will be enrolled in Part B; but if emerging data suggest alternative indications should be pursued, then participants with ovarian, esophageal, TNBC or other indications as deemed fit may be considered.

- Tumor biopsy samples

[REDACTED]

9.3 POPULATIONS FOR ANALYSES

For purposes of analysis, the following populations are defined in [Table 12](#).

Table 12 Analysis Populations

Analysis Population	Description
Efficacy	All participants who received at least one dose of RO7296682, and who have at least one baseline and one on-study tumor assessment. Participants who received at least one dose of study drug and discontinued the study because of progression before the first on-study tumor assessment will be considered as response-evaluable.
DLT evaluable	DLT evaluable participants are those who have completed the DLT period with two administrations of RO7296682 during the DLT period and without DLT, or participants reported with a DLT. This population will be used in the determination of the MTD and/or RP2D.
Safety	All participants randomized to study treatment (RO7296682) and who received at least one dose of the study treatment, whether prematurely withdrawn from the study or not, will be included in the safety analysis.
Pharmacokinetic	All participants who have received at least one dose of study treatment (RO7296682) and who have data from at least one post-dose sample will be included in the PK analysis population. Participants will be excluded from the PK analysis population if they significantly violate the inclusion or exclusion criteria, deviate significantly from the protocol, or if data are unavailable or incomplete which may influence the PK analysis. Excluded cases will be documented together with the reason for exclusion. All decisions on exclusions from the analysis will be made prior to database closure.
Immunogenicity	The immunogenicity analyses will include all participants with at least one ADA assessment, irrespective of whether or not the participant receives any treatment. Excluded cases will be documented together with the reason for exclusion.

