4.1.3 Dose-Limiting Toxicities

A DLT is defined as a clinically significant AE (classified according to the NCI CTCAE v.5.0, as applicable) or significant laboratory abnormality if all of the following events apply:

- occurring during the DLT assessment period as defined in Section [4.1.2.1](#); and
- considered to be related to study treatment RO7296682 by the Investigator, and
- is not attributed to disease progression or another clearly identifiable cause

During the dose escalation phase, participants who withdraw before the end of the DLT period, for reasons other than DLTs, and participants who did not receive two doses of RO7296682 will be replaced to ensure that at least 3 DLT evaluable participants have been assessed prior to moving to the next dose level (see Section 7.1 for replacement rules). The DLT will be counted for each dose separately and each participant will contribute one single representative data point to the EWOC design.

The following AEs are considered DLTs:

Hematological toxicities defined as:

- Grade 4 neutropenia (ANC of $<500/\mu\text{L}$) lasting ≥ 7 days
- Grade ≥ 3 febrile neutropenia
- Grade 4 thrombocytopenia lasting ≥ 48 hours
- Grade 3 thrombocytopenia associated with significant bleeding episode and/or bleeding episodes requiring platelet transfusions
- Grade 4 anemia

Any non-Hematological toxicities Grade ≥ 3 except for:

- Grade 3 nausea, vomiting, or diarrhea that resolves to Grade ≤ 1 with or without treatment and which resolves within one week
- Grade ≥ 3 fatigue that resolves to Grade ≤ 2 within 7 days
- Grade 3 arthralgia that can be adequately managed with supportive care or that resolves to Grade ≤ 2 within 1 week
- Fever >40 degrees Celsius that occurs within 48 hours of RO7296682 infusion and resolves to $<$ Grade 2 within 48 hours and is fully resolved within 7 days
- Grade ≥ 3 laboratory abnormality that is asymptomatic and deemed by the Investigator not to be clinically significant
- Grade 3 autoimmune thyroiditis or other endocrine abnormality that can be managed by endocrine therapy or hormonal replacement
- Grade 3 tumor flare defined as local pain, irritation, or rash localized at sites of known or suspected tumor

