9.4.2 Efficacy Analyses

The primary and secondary efficacy analyses listed in [Table 13](#) will include all participants in the efficacy population with participants grouped according to dose cohort (and schedule if applicable) within each study part.

Table 13 Efficacy Statistical Analysis Methods

Endpoint	Statistical Analysis Methods

According to RECIST Version 1.1 criteria (Appendix 7) and iRECIST (Appendix 8)
 
 • Objective response rate (ORR) • Disease control rate (DCR) • Duration of response (DoR) • On treatment progression free survival (PFS) 	
No formal statistical model and no formal hypothesis testing are planned in this study. Tumor response data will be reported using descriptive statistics. Response data will be listed. Participants with missing or no response assessments will be classified as not evaluable unless there is documented clinical deterioration, in which case participant will be classified as non-responders. Reasons for the non-evaluability will be summarized (e.g., withdrawal of consent, study discontinuation because of AE or physician decision). ORR and DCR will be summarized by using relative frequencies and 90% confidence interval (CI). Duration of response and PFS (on-treatment) will be summarized by using time-to-event analyses and Kaplan-Meier curves.

 • Overall Survival (OS) (if available) 	
OS data may be tabulated and summarized using time-to-event analyses and Kaplan-Meier curves if data are collected and mature.
 
Summaries will be carried out by cohort (and schedule if applicable) separately for each part.

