Objective response rate (ORR) is determined as the rate of participants with an overall response of CR or PR. Disease control rate is determined as the rate of participants with an overall response of either CR, PR, or SD rate. ORR and DCR will be derived for RECIST Version 1.1 and will be based on Investigators' assessment. Objective response (OR) is defined as a CR or PR as determined by the Investigator. For this protocol, confirmation of response is required at least 4 weeks after a first response occurred. To classify a response as SD, measurements will have to be classified as stable (according to RECIST Version 1.1) at least once after study entry at a minimum of 6 weeks after study entry. Participants with missing or no response assessments will be classified as not evaluable unless there is documented clinical deterioration, in which case participant will be classified as non-responders.

DoR will be calculated for participants who have a best overall response of CR or PR and will be defined as the time from first occurrence of a documented OR until the time of documented disease progression or death (death within 30 days from last study

treatment) from any cause, whichever occurs first. Censoring methods will be the same as the one applied for progression-free survival (on-treatment PFS).

PFS on treatment will be defined as the time from study treatment initiation (C1D1) to the first occurrence of documented disease progression (based on RECIST Version 1.1 Investigator's assessment) or death from any cause, whichever occurs first. For participants who do not have documented progressive disease or death (within 30 days from last study treatment) during the study, PFS will be censored at the day of the last tumor assessment. Participants without any post baseline assessments or with all post-baseline assessments having unknown result/response but known to be alive at the clinical cut off for the analysis will be censored at the date of study treatment initiation plus one day.

Sensitivity analyses of response endpoints (ORR, DRC, DoR, and PFS) may include the evaluation of response according to iRECIST. As a sensitivity analysis, the analysis described in [Table 13](#) may be applied to a more generic definition of PFS that also includes deaths occurring more than 30 days after last study treatment. Secondary analyses of response endpoints may (if implemented) include the evaluation of response.

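### The efficacy population leaves out treated participants who exit before any on-study scan for reasons other than progression, which can raise ORR and DCR but never lower them

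*Combined protocol and SAP*

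**What the plan says.** Table 12 (Section 9.3) sets the main rule for the efficacy population: "All participants who received at least one dose of RO7296682, and who have at least one baseline and one on-study tumor assessment". The one stated exception is for treated participants who "discontinued the study because of progression before the first on-study tumor assessment will be considered as response-evaluable".

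Section 9.4.2 says the analyses in Table 13 "will include all participants in the efficacy population with participants grouped according to dose cohort". Table 13 lists ORR, DCR, DoR, on-treatment PFS and, if available, OS.

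Three rules in Section 9.4.2 then deal with absent assessments or define the rate:

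- Response: "Participants with missing or no response assessments will be classified as not evaluable unless there is documented clinical deterioration", in which case the participant is a non-responder.
- Reporting: "Reasons for the non-evaluability will be summarized (e.g., withdrawal of consent, study discontinuation because of AE or physician decision").
- PFS: "Participants without any post baseline assessments or with all post-baseline assessments having unknown result/response but known to be alive" at the clinical cut-off are censored at treatment start plus one day.

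The rate itself is defined as follows: "Objective response rate (ORR) is determined as the rate of participants with an overall response of CR or PR". No response analysis on all treated participants is planned. The sensitivity analyses in Section 9.4.2 cover iRECIST and a PFS definition that counts later deaths.

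**The concern.** Apart from the progression exception, entry to the efficacy set depends on something that happens after treatment starts: reaching an on-study scan. A participant who has none, and did not leave for progression, is absent from the denominator as well as the numerator. CR and PR need a scan, and Section 9.4.2 requires stable disease to be seen at least 6 weeks after entry. The exclusion therefore works in one direction on ORR and DCR. For PFS and OS it removes deaths that those endpoints would otherwise count.

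The rules for absent assessments also fit the set loosely. They are worded as if unscanned participants were in it, and the listed reasons (consent withdrawal, AE, physician decision) are not progression. A participant who leaves for one of those reasons and is never scanned has already been removed by Table 12.

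At stake is how the first activity estimates for this antibody read, especially by dose cohort, where denominators are small.

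**Working it through.** The plan gives no expected ORR, DCR or dropout figure, so there is nothing to reproduce.

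**Who is left out.** The first scheduled on-treatment scan is 8 weeks (± 7 days) after first dose (Table 1, footnote o). Participants who stop for reasons other than progression are still due a scan at Safety Follow-Up, and at end of treatment if the last one was at least 28 days earlier (footnotes o and r). The remaining group is mainly people who, before any scan:

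- die without attributed progression;
- withdraw consent, after which Section 7.2 allows no follow-up; or
- are lost to follow-up.

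**Direction.** Let N be the number treated, d the number excluded and x the number with response (or disease control). Excluded participants cannot be in x. The rate moves from x/N to x/(N − d), a factor of N/(N − d) ≥ 1. Enumerating N = 1 to 90 with every feasible d and x gave 129,675 combinations. The rate rose in 121,485, was unchanged in 8,190 (d = 0 or x = 0) and never fell.

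**Size.** N = 50 is the Part B ceiling (Section 9.2). All values of x and d, and the cohort of 6, are assumptions. The plan asks for 90% intervals without naming a method; exact (Clopper-Pearson) intervals are used here.

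| Set | d | ORR (90% CI) | DCR (90% CI) |
|---|---|---|---|
| Part B, N = 50 | 0 | 6/50 = 12.0% (5.4–22.3) | 20/50 = 40.0% (28.3–52.6) |
| | 1 | 6/49 = 12.2% (5.5–22.7) | 20/49 = 40.8% (28.9–53.6) |
| | 2 | 6/48 = 12.5% (5.6–23.2) | 20/48 = 41.7% (29.6–54.5) |
| | 3 | 6/47 = 12.8% (5.7–23.6) | 20/47 = 42.6% (30.3–55.6) |
| Dose cohort of 6 | 0 | 1/6 = 16.7% (0.9–58.2) | 3/6 = 50.0% (15.3–84.7) |
| | 1 | 1/5 = 20.0% (1.0–65.7) | 3/5 = 60.0% (18.9–92.4) |

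With no responders the estimate stays at 0% and only the upper limit moves, for example from 5.8% at n = 50 to 6.4% at n = 45.

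**Not-evaluable members.** Suppose 2 of 50 are unscanned and 3 have unreadable scans.

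- All treated: ORR 6/50 = 12.0%, DCR 20/50 = 40.0%.
- Table 12 set with the not-evaluable kept in: 6/48 = 12.5% and 20/48 = 41.7%.
- Table 12 set with them left out: 6/45 = 13.3% and 20/45 = 44.4%.

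**Time-to-event endpoints.** Censoring a living participant at treatment start plus one day removes that person from the risk set before any later event. In the worked examples this gave the same Kaplan-Meier estimate as exclusion. A non-progression death within 30 days of last treatment is different, because the on-treatment PFS rule counts it as an event. With 15 of 50 event-free at 6 months and no censoring (assumed), dropping one such death moves 15/50 = 30.0% to 15/49 = 30.6%; dropping two gives 15/48 = 31.3%. The same deaths leave OS. DoR is calculated only in responders, all of whom have scans, so it is unaffected.

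**The case against.** **The rules do not contradict each other.** A reader might infer that the not-evaluable and censoring rules cannot coexist with Table 12. They can, because each has work to do inside the set:

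- Incomplete or unreadable scans can be not evaluable (Appendix 7, Section 2.4.2).
- A participant who stops early may have a stable scan before 6 weeks, too soon to count as SD, and the reason for stopping may well be an AE or consent withdrawal.
- Members of the progression exception may have no scan at all, for example after symptomatic deterioration (Appendix 7, Section 2.4.3).

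This objection stands. The wording is a loose fit, not a contradiction.

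**Section 4.1.3 does not show that anyone goes unscanned.** It foresees "participants who withdraw before the end of the DLT period, for reasons other than DLTs", and that period ends about day 29, before the week 8 scan. It is tempting to read this as proof of an excluded group. But it is a replacement rule, its reasons include progression, which Table 12 keeps, and post-discontinuation scans are scheduled.

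**The denominator is not really open.** Section 9.4.2 says all members of the efficacy population are included, which implies that not-evaluable members stay in. The lowest-denominator figures above (13.3% and 44.4%) need the opposite reading. An explicit sentence would be confirmation. If those members were left out anyway, Table 12 would add no further shift.

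**Early exits are visible elsewhere.** Disposition (Section 9.4.1) and deaths and premature withdrawals from treatment (Section 9.4.3, Table 14) are summarized on the safety population, so a reader could rebuild an all-treated rate.

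**A response-evaluable set is a legitimate choice** in a Phase 1 study with no hypothesis test (Section 9.1). That is a reason to keep it as supportive. It does not remove the one-way effect when it is the only set planned.

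**Conclusion.** The point holds as a minor to moderate one. Table 12 excludes treated participants with no on-study scan unless they left because of progression. It is the only set planned for these endpoints, and the exclusion can raise ORR and DCR or leave them unchanged, never lower them. Unscanned non-progression deaths are also lost from PFS and OS.

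The direction follows from the definitions, provided not-evaluable members stay in the denominator. The size does not: the documents give no dropout figure and do not say whether a post-treatment scan counts as on-study. On the assumed counts, Part B ORR shifts by 0.2 to 0.8 points against a 90% interval about 17 points wide, and DCR by 0.8 to 2.6 points. One exclusion in a cohort of 6 moves ORR by 3.3 points and DCR by 10, again within very wide intervals.

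A reader might infer that the activity results are materially biased or that a dose decision is at risk. The documents support neither. These endpoints are secondary or, for OS, exploratory; all are descriptive, and the MTD is estimated from DLT-evaluable participants.

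**What to change.** - Use all participants who received at least one dose as the denominator for ORR and DCR and as the analysis set for PFS and OS.
- Confirm in Section 9.4.2 that not-evaluable participants stay in the ORR and DCR denominators, reported as a separate category with reasons. The non-responder label for documented deterioration can stay.
- Keep the current Table 12 definition as a supportive response-evaluable set.

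This changes wording only and needs no new data. The cost is slightly less favourable reported rates, or no change from the new denominator if nobody is unscanned.
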